### 6.4.2 Qualitative data

We will conduct focus groups and in-depth interviews at each site (via telephone or face-to-face) to obtain feedback from participants, line managers, HR and OH staff. Topic guides will

focus on the intervention content and process; how recruitment and delivery methods work in practice; and suggestions for improvement.

Where possible, we will conduct one-to-one in-depth interviews with at least two and a maximum of three study participants per study centre. Where possible, pilot interviews will be carried out prior to the main study to assess comprehension, relevance and appropriateness of the interview schedule. We will conduct two focus groups at each of the six study centres, employing purposes sampling to recruit a group of OH nurses (including those trained in case management), and a group of HR and line managers. There will be a total of 12 focus groups with 5 to 8 members per group. All focus groups and interviews will be audio-taped, last approximately one hour and will take place in a convenient location at each site. The focus groups and interviews will be conducted by one of the research team members (post-doc trained). Sessions will be recorded on an audio-recorder and transcribed verbatim shortly after each session by a fully skilled medical secretary employed by the Guy's and St Thomas' NHS Foundation Trust. Audio recordings will not be deleted after transcription and will be kept for the duration of 20 years. No identifiable information will be included during the transcription process. Transcripts will be stored electronically using password protection.

Distress protocol: The research team members conducting the individual and focus group sessions are qualified psychologists and have experience providing counselling support. In circumstances where a participant in the individual or focus group interviews become upset or distress, the research team will be able to provide them with immediate support in addition to providing the participant with information about local services and resources. In addition, the interviewers are backed up by co-investigators with extensive clinical experience in occupational medicine and occupational psychiatry. Where appropriate we will be able to liaise with participant's GP or alternatively secondary clinical services to facilitate an appointment/referral. We will also take a number of different measures to prevent and minimise upsetting the respondents for example e,g. participants will be given the option to skip questions, should the participant decided that they do not wish to answer. Participants will be informed during the consent stages that they are free to withdraw from the study at any stage without giving a reason.

The end of the study will be the last participant last interview.

### 6.5 Data analysis

For the purpose of the intention to treat (ITT) analysis, participants will be considered as entered into the study upon completion of the baseline questionnaire.

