### 1.0 Summary of research

**Design:** A mixed methods study to develop and test the feasibility of an intervention to improve return to work in NHS staff who go on sick leave with a CMHD.

Method: The study is divided into 2 phases:

- Phase 1 aims to test the feasibility and acceptability of the intervention in the NHS
  and to assess for contamination if the main trial were to be a randomised controlled
  trial at departmental level.
- Phase 2 finalises the manualised intervention and makes recommendations on the best study design for a future trial.

A significant amount of preparatory work was completed prior to phase 1/2 and a full description of this work can be found in the appendix.

We will carry out phase 1 in six OH departments (study centres). At three study centres, study participants will be assigned either to see an OH nurse who has been trained as a case-manager and will receive the intervention or to see an OH nurse who has not been trained as a case-manager and will receive CAU. At two centres, participants will receive CAU only and at one centre, participants will be assigned an OH nurse who has been trained as a case-manager. This design allows us to test for feasibility of the intervention in a NHS setting and to assess the risk of contamination if a cluster RCT were undertaken.

**Setting:** Six OH departments delivering services to different types of NHS Trusts. **Target population:** NHS staff who have recently been issued with a fit note which includes a CMHD.

**Inclusion criteria:** Staff with a CMHD with or without an associated physical disorder, who have been off sick for more than 7 days and fewer than 90 days. Employee must be off sick when referral made to OH and when completing baseline questionnaire.

**Exclusion criteria:** Staff with a psychotic disorder, bipolar disorder, substance misuse disorder or dementia. Staff under investigation for misconduct or in the process of formal disciplinary action.

**Health technologies being assessed:** Standardised case management delivered by OH nurses following training. The intervention is likely to include identifying barriers to RTW, problem solving, peer-support networking, work-focused CBT, optimisation of clinical treatment and goal setting. An agreed written RTW plan with workplace adjustments, based on discussion between participants and their manager and shared with the participants' healthcare professionals. Regular timed reviews.

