# **WB2W Study: STUDY FLOWCHART**

# Intervention arm

# Care as usual arm

ACTIVITY (does not apply to employees who self-refer): Line manager receives fit note & refers to OH if worker agrees. Where possible, line manager gives participant information sheet (PIS) to employee. The PIS may also be sent directly to prospective participants from the occupational health team once the referral to OH ETURN TO WORK has been made. Ideally line manager immediately phones case manager to make the referral for OH follow-up otherwise the referral is made by email on the same day. (Sites will be requested to disseminate specific wording locally aimed at raising the profile of OH and their involvement in the study) ACTIVITY (Where possible, PHONE CALL from OH to worker within 3 working days of OH referral): Confirms eligibility and sends PIS if not already received OH worker books 1st app. Participant receives baseline questionnaire by post and/or email manager Sites will have the option of sending a participant

Participant receives care as usual (non-participant questionnaire sent to those who do not wish to participant in the study

Does not wish to

take part in the

study

Not eligible or

does not want to

take part

Sites will have the option of sending a participant information sheet along with appointment details to all new referrals who are booked into see a local field workers. This will provide an opportunity for field workers to screen and recruit participants who are assessed as meeting the inclusion criteria during the 1st appointment

0m questionnaire

Participant receives care as usual

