# During 1st OH appointment

Check participant has completed baseline questionnaire. If not completed, baseline questionnaire should be completed at 1st appt

- OH nurse confirms eligibility
- OH nurse takes written consent (if 1st appointment occurs via telephone, verbal consent will be documented on the consent form)
- Participant information sheet if not already received

3m questionnaire

6m questionnaire

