We will collect the same data on all participants and participating centres. Data from all groups will be used to answer questions about rates of recruitment and follow-up, and the acceptability and performance of methods to assess possible outcome measures. Data from Group A and Group D will provide information about the acceptability and costs of the intervention, and rates of adherence to the intervention. Data from Groups B and C will provide information about the distribution of possible outcome measures in the absence of the intervention (which would help in power calculations for a subsequent trial). Comparison of the management of participants in Groups B and C will give an indication of potential for major "contamination". The follow-up period will be six months from recruitment. Outcomes will be assessed using a mix of qualitative and quantitative methods.

Target population: NHS staff who have recently commenced sick leave because of CMHD

**Inclusion criteria:** Staff with CMHD with or without an associated physical disorder who have been off sick for a period of more than 7 days (i.e. on receipt of fit note) and less than 90

days. Staff will be screened for eligibility for entry into the study either at the time of referral to OH or during their 1st OH appointment.

**Exclusion criteria:** Staff with a psychotic disorder, bipolar disorder, substance abuse or dementia. Staff under formal investigation for misconduct or in the formal process of disciplinary action (as this may be an effect modifier).

Six OH departments have been chosen from those confirming that they wished to participate in the feasibility study in response to the questionnaire sent to the current SCIN study centres plus one ambulance trust. We have selected NHS OH departments representative of the range of NHS Trusts in the UK, providing OH services to a mixture of acute, mental health and ambulance trusts. All trusts included have electronic OH data capture systems, do not currently have early (<8 day) intervention for sickness absence or case-management in use and employ more than two OH nurses who advise on RTW in workers with CMHD.

We have allocated the participating trusts to care as usual or mixed intervention/ care as usual centres / intervention centre based on sampling groups with the aim of achieving broad comparability between the types of trust.

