### 11.0a Governance and legal compliance

) We will apply for Health Research Authority approval study. . We will apply for Research and Development (R&D) approval via the new Health Research Authority's system and R and D approval from each centre via the site specific forms.

Although 49 of the participants will not receive the intervention, they will receive care as usual for their Trust. The participating centre will benefit from help with standardising the data collection of their sickness absence. Our experience from the SCIN trial and other studies in NHS staff has been that NHS staff are keen to participate in research studies which aim to improve the health of NHS staff, provided that questionnaires do not take too long to complete. NHS staff understand the importance of collecting data from participants who may not receive the intervention. Our experience is that NHS staff embrace the concept that 'research is everyone's business.'

Participants who receive the intervention, but have not returned to work after six months, will, at the discretion of the participating centre, continue to receive the intervention until they return to work. Our data on RTW times for NHS staff who go on sick leave with CMHD suggests that most of the participants are likely to have RTW by six months after being recruited into the study.

Approval for the study will be obtained in advance from the management and staff representatives at the participating trusts. Informed consent will be sought from all staff participants before entry into the study. If first occupational health appointment occurs face to face, OH nurse will take written informed consent at the commencement of the first appointment; if first OH appointment occurs by telephone, OH nurse will take informed consent at the commencement of the first telephone consultation and verbal consent will be documented on the consent form..Data collection will be organised such that names and contact details of individuals who take part in the study are held separately from other personal information, which will be identified only by a serial number. No information will be published in a form that could lead to the identification of individuals.

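### Study entry for the ITT set is fixed at completion of the baseline questionnaire, which on the expected route comes before consent and the final eligibility check

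*Protocol*

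**What the plan says.** Four parts of the Protocol bear on the moment of entry.

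- **Section 6.5 (Data analysis).** For the ITT analysis, "participants will be considered as entered into the study upon completion of the baseline questionnaire". What counts as completion is not defined.
- **Study flowchart.** An occupational health phone call, made where possible, comes first: "Confirms eligibility and sends PIS if not already received". The first appointment is then booked and "Participant receives baseline questionnaire by post and/or email". At that appointment the nurse checks that the form has been done: "If not completed, baseline questionnaire should be completed at 1st appt". At the same visit "OH nurse confirms eligibility" and consent is taken.
- **Section 11.0a.** "Informed consent will be sought from all staff participants before entry into the study". The section places consent at the start of the first appointment, in writing if face to face and verbally with documentation if by telephone.
- **Section 6.4.1.** The baseline form belongs to entry, t=0. The 3- and 6-month forms and the six months of staff-record (ESR) absence data are counted from entry.

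Section 6.1 adds that staff are "screened for eligibility for entry into the study either at the time of referral to OH or during their 1st OH appointment". Section 1.0 lists completeness of the data collected among the feasibility outcomes.

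**The concern.** An analysis set should be fixed by events that make a person a participant, which are consent and eligibility. Here it is fixed by the return of a data-collection form. Three things follow.

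1. The entry rule conflicts with the consent rule. Someone who returns the posted form in good time has entered under section 6.5 before giving the consent that section 11.0a requires first.
2. The ITT set can be wrong in both directions. It can take in people who return the form and then decline or are found ineligible. It leaves out people who consent, and may start the intervention, without completing the form.
3. The start of follow-up moves with the form. It falls before the appointment for those who reply early, and at the appointment for those who complete the form there.

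This matters because the study exists to measure how well recruitment, data collection and follow-up would work in a full trial (section 4.1, question 7). An entry rule that requires a baseline form removes baseline non-return from view.

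**Working it through.** **Sequence on the expected route**

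| Step | Event | Source |
|---|---|---|
| 1 | Phone eligibility check, where possible | Flowchart |
| 2 | Appointment booked; baseline form posted or emailed | Flowchart |
| 3 | Form completed, so the person has entered and t=0 is set | 6.5 with 6.4.1 |
| 4 | First appointment: consent taken, eligibility confirmed | Flowchart; 11.0a |

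Section 11.0a requires step 4 consent to precede entry, but section 6.5 puts entry at step 3. The order does not rest on the layout of the flowchart: the instruction to check for an already completed form at the appointment shows that completion beforehand is expected. If the form is instead completed at the appointment after consent, the conflict disappears, so it depends on route.

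**The plan's own figure**

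Section 6.6 states that 60 participants estimate an 80% participation rate to within 10 points. With n = z²p(1−p)/d², z = 1.96, p = 0.80 and d = 0.10:

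1.96² × 0.80 × 0.20 / 0.10² = 61.5, or 62 rounded up.

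The half-width 1.96 × √(0.16/n) is 10.1 points at n = 60 and 8.9 points at the maximum of 77. The stated figure is reproduced closely, and the entry definition does not touch it.

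**Effect on completeness (assumed rates)**

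The Protocol gives no rate of baseline non-completion. Take 77 consented, eligible staff and assume that 0, 5, 10 or 20% never complete the form, rounded to whole people. Assume also that about 75% of those counted as entered return a follow-up form, and that those not entered return none.

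| No baseline form | Entered under 6.5 | Form held, of entered | Form held, of consenters | Follow-up, of entered | Follow-up, of consenters |
|---|---|---|---|---|---|
| 0 | 77 | 100% | 77/77 = 100% | 58/77 = 75.3% | 58/77 = 75.3% |
| 4 | 73 | 100% | 73/77 = 94.8% | 55/73 = 75.3% | 55/77 = 71.4% |
| 8 | 69 | 100% | 69/77 = 89.6% | 52/69 = 75.4% | 52/77 = 67.5% |
| 15 | 62 | 100% | 62/77 = 80.5% | 46/62 = 74.2% | 46/77 = 59.7% |

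The third column cannot vary, because holding a form is the condition for being counted.

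**Effect in the other direction (assumed numbers)**

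If 4, 8 or 15 people complete the form and then decline or prove ineligible, on top of 77 valid participants, their share of the literal ITT set is 4/81 = 4.9%, 8/85 = 9.4% or 15/92 = 16.3%.

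**The case against.** The strongest reply is that the study is descriptive, specifies no effect test on the ITT set, and already limits the damage. Much of that stands.

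- **Few consenters should lack a form.** The flowchart has a missing form completed at the appointment where consent is taken. A gap is most plausible for telephone appointments. One can build a starker example, with 77 consenting, 65 completing baseline and 55 returning the six-month form, which gives 55/65 = 85% against 55/77 = 71%. That assumes 12 of 77 (16%) without a form and is illustration only.
- **Eligibility is checked earlier.** A reader might infer that forms go to unscreened staff. The phone call is meant to confirm eligibility before the form is sent, though only where possible. What can come after the form is the final confirmation.
- **Decliners have their own path.** The flowchart gives exits for people who are ineligible or unwilling. Placing them in the ITT set is the literal reading of section 6.5 and probably not the intended one, but nothing in that section excludes them.
- **Not every rate is affected.** A reader might infer that people without a form vanish from all denominators. Section 6.5.1 bases the recruitment rate on eligible staff and those who agree, and does not tie the completion proportions explicitly to the ITT set.
- **Baseline data are not 100% complete by construction.** Section 6.5.1 quantifies missing data for each outcome measure, and a returned form can have blank items. Only possession of a form is fixed.

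Two neighbouring points do not add to the case. Section 1.0 requires that "Employee must be off sick when referral made to OH and when completing baseline questionnaire"; section 6.1 does not repeat this but says nothing contrary. And the absence table in section 2.3 gives 30.86/(30.86 + 47.91) = 39% of absences of 7 days or more falling in the 7 to 28 day band. A reader might infer that many people return to work between referral and baseline, but the figure does not measure that interval, which the Protocol nowhere quantifies.

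**Conclusion.** The concern holds in a limited form. On the expected route, the entry rule in section 6.5 and the consent rule in section 11.0a contradict each other, and section 6.4.1 makes the time origin depend on when the form is completed. The size of the consequence is unknown. Under assumed baseline non-completion of 0 to 20%, form-level completeness over consenters is 100% down to 80.5%, against a constant 100% over those entered. Given the in-appointment fallback, the low end of that non-completion range is more likely. The effect on follow-up rates rests on the further assumptions that completeness is reported over the ITT set and that people not entered return nothing. No size can be given for the shift in the start of follow-up. The sample-size statement, the recruitment rate and item- or measure-level missingness are unaffected.

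**What to change.** - In sections 6.5 and 6.4.1, define entry and t=0 as the date on which consent has been given and eligibility confirmed, for every recruitment route including recruitment during the first appointment.
- Report possession of a baseline form, follow-up return and complete data sets over all consented, eligible staff, and say what counts as a completed baseline form.
- Time the 3- and 6-month forms and the ESR window from that date.
- Reconcile the flowchart and sections 6.4.1, 6.5 and 11.0a. In particular, state whether a posted form may be completed before consent and, if so, what happens to it when the person then declines or is ineligible. This needs an explicit answer because section 6.4.1 collects contact details with the baseline form.

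The cost is a change of wording, with no effect on the sample size. Reported completeness may come out slightly lower, but it will then describe everyone who agreed to take part.

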# 6.5.1 Quantitative

Rates of recruitment will be calculated from the numbers of eligible participants and of those who agree to participate in the study. Characteristics of eligible participants will be recorded at baseline and will be summarised through means, medians, standard deviations, and interquartile ranges (IQRs). Characteristics will be compared between those who agree to participate in the feasibility study and those who do not. Outcome variables, including anxiety/depression score, health related quality of life score, use of antidepressants, will be summarised separately for baseline and follow-up using means and standard deviations if they are normally distributed, or through medians and IQRs otherwise. Number of days before returning to normal working hours will be summarised by medians and IQRs. For each possible outcome measure, the prevalence of missing data will be quantified. We will calculate the proportion of participants who complete the intervention, and the proportion of completed data sets.

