### 2.4.1 Clinical outcomes

Clinical improvement in CMDs such as reduction in the number or severity of symptoms can be captured with a number of well-established assessment tools. We will use the PHQ-9 and GAD-7 because: they are brief and designed to be completed by the patient; changes in their scores accurately reflect improvement and worsening of symptoms of depression and anxiety: and they are free to use (Kroencke 2001, National Institute for Health and Care Excellence 2011). Furthermore, PHQ-9 is used by GPs and practitioners involved in the Improving Access to Psychological Therapies (IAPT) initiative, giving us an opportunity to compare the outcomes of this study directly with routine care in non-NHS workers. In addition, we will collect information on adherence and change in use of medication.

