# 6.4 Data collection and follow up 6.4.1 Quantitative data

Data on sickness absence for CMHD will be collected for six months after the participant enters the study from S10 on the participating centre's ESR and by self-report questionnaire. Study participants will be given a self-administered baseline questionnaire to complete at the time of entry to the study (t=0). They will be sent a follow-up self-administered intermediate questionnaire at three months (T=3) and a final follow-up self-administered questionnaire at six months (t=6) after entry to the study. Note, all participants will complete the same baseline and intermediate questionnaires. Responses provided in the intermediate questionnaire will than determine which version of the final questionnaire will be administered i.e. final questionnaire (version 1) will be administered to those employees who are back at work in any capacity for more than four weeks at the three month time point (T=3); final questionnaire (version 2) will be administered to those who are still off on sick leave at T=3months due to their mental health condition (including those who have not returned to sustained work) or those who did not return the intermediate questionnaire.

Participants will be invited to complete paper-based questionnaires. This will be returned to the central research team using business reply envelopes. A series of reminders will be used to encourage return of the study questionnaires for non-responders. The reminders will include, one email reminder, one telephone reminder and finally a replacement questionnaire will be sent to the participants preferred postal address. To allow to send participants 3 and 6 months questionnaires (and reminders if needed), we will collect contact details from participants (name, surname, mobile phone, email address, home postal address). Contact details will be collected together with the baseline questionnaire.

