We will collect information about: rates of recruitment; reasons for non-participation; baseline characteristics of those eligible for inclusion; adherence to the intervention in those allocated to receive it and the management of those who are not; and rates of successful follow-up. Additionally, we will collect data on the distribution of possible outcome measures, including, reduction in anxiety/ depression, health-related quality of life, change in antidepressant use and RTW during the six month study period. Full and partial return to work will be measured by total days of sickness absence before return to work and self-reported number of hours worked. We will collect information about participants' referral to and uptake of improving access to psychological therapies (IAPT) services and the Government's Fit for Work Service We will record any protocol violations, reasons for not completing the intervention and any adverse events.

At the sponsor site (Guy's and St Thomas NHS Foundation), we will conduct further exploratory work to better understand the factors impacting on the identification and referral of employees who are on sick leave with a common mental health disorder. Where appropriate and with relevant permissions, this may include reviewing information on existing management referrals. These insights will be pooled with information obtained from the focus group interviews.

Costs of delivering the package of interventions including OH nurse time, participant and manager time and cost of training OH nurses in case management.

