### 7.0 Phase 2:

Finalisation of the manualised intervention and recommendations for design of a RCT

**Method:** We will work with our stakeholder group including our PPIs to review the information from the feasibility study and determine whether a cluster RCT could be designed that was free from unacceptable contamination. We will review the findings from qualitative, quantitative and economic analyses. We will pay particular attention to the response rate, and likelihood of contamination to determine if an individual or cluster trial would be the most appropriate method for a definitive trial.

Should a RCT be judged feasible, data from the feasibility study on the distribution of relevant outcome measures in the absence of intervention will help to inform power calculations.

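### If antidepressant use is recorded yes/no, the mean-or-median rule in section 6.5.1 does not report the proportion using: 13 and 24 users of 49 both print as 0 (IQR 0 to 1)

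*Protocol*

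**What the plan says.** Section 6.5.1 groups three kinds of outcome (anxiety/depression score, quality-of-life score and antidepressant use) under one instruction: "use of antidepressants, will be summarised separately for baseline and follow-up using means and standard deviations if they are normally distributed". Where that condition fails, the median and IQR are to be given instead. In that section, proportions are planned for recruitment, completion of the intervention, missing data and completed data sets. No count or percentage is planned for antidepressant use.

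The coding of the variable is not given. Section 2.4.1 says "we will collect information on adherence and change in use of medication", and section 6.4.1 lists "change in antidepressant use and RTW during the six month study period" among the possible outcome measures. Neither says whether the record is yes/no, a number of drugs or a dose.

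The summaries have a stated later use. Section 6.1 wants outcome distributions from the care-as-usual groups (B and C), and section 7.0 says that "data from the feasibility study on the distribution of relevant outcome measures in the absence of intervention will help to inform power calculations". The outcomes envisaged for the definitive trial in section 6.1 include change in medication for mental illness.

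**The concern.** A mean with SD, or a median with IQR, suits the PHQ-9, the GAD-7 and a quality-of-life score. It does not suit a yes/no item. Such an item is never normally distributed, so the test built into the rule steers to median and IQR. For a 0/1 variable these can take only a handful of values, and none of them is the proportion of users. The mean of a 0/1 variable is that proportion, so the rule discards the one summary in it that would have kept the information.

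This is a rule that the protocol states for a named variable, so it is more than a detail left open. At stake is the proportion on antidepressants without the intervention, which a later trial would need in order to plan around medication use.

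**Working it through.** **Inputs.** Section 6.1 plans Group B = 21 and Group C = 28, both receiving care as usual. 21 + 28 = 49, which matches the 49 that section 11.0a says will not receive the intervention. The protocol gives no figure for antidepressant use, so every possible number of users, k, is considered. Yes/no coding (1 = using, 0 = not using) is an assumption.

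**Quartiles of a 0/1 variable, n = 49.** Sorted, the data are 49 − k zeros followed by k ones, so the value at position j is 1 exactly when k ≥ 50 − j. Under the common linear definition, quantile p sits at position 1 + (n − 1)p:

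- Lower quartile: 1 + 48 × 0.25 = position 13, which is 1 when k ≥ 37.
- Median: 1 + 48 × 0.50 = position 25, which is 1 when k ≥ 25.
- Upper quartile: 1 + 48 × 0.75 = position 37, which is 1 when k ≥ 13.

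| Users of 49 | Percentage | Printed median (IQR) |
|---|---|---|
| 0 to 12 | 0% to 24% | 0 (0 to 0) |
| 13 to 24 | 27% to 49% | 0 (0 to 1) |
| 25 to 36 | 51% to 73% | 1 (0 to 1) |
| 37 to 49 | 76% to 100% | 1 (1 to 1) |

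Fifty possible counts give four printed results. Eleven more users, from 13 to 24, change nothing. One more, from 24 to 25, moves the median from 0 to 1.

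**Sensitivity to the quantile definition.** Nine standard definitions were run. Seven give 0 (0 to 1) for exactly 13 to 24 users. The closest-observation definition gives it for 13 to 25. The interpolated inverted CDF gives it for 14 to 24, because at 13 users its upper quartile is 0.75. So 13 and 24 users print alike under eight of nine, and 14 (28.6%) and 24 (49.0%) under all nine.

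**What a count and percentage would show.** 13/49 = 26.5% and 24/49 = 49.0%. The 95% Wilson interval is (p + z²/2n ± z√(p(1 − p)/n + z²/4n²)) / (1 + z²/n). With z = 1.96 and n = 49:

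- p = 0.2653: (0.3045 ± 0.1297) / 1.0784, or 16.2% to 40.3%.
- p = 0.4898: (0.5290 ± 0.1454) / 1.0784, or 35.6% to 62.5%.

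**Other codings.** For number of drugs (one or two per user), the upper quartile is the (k − 12)th lowest value among users. The print is therefore still 0 (0 to 1) if at least k − 12 users take one drug: 1 of 13, or 12 of 24. For dose, the median is 0 for any k from 0 to 24, but the upper quartile is the (k − 12)th lowest dose and can move, so the two cases need not print alike.

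**The case against.** The strongest reply is that section 6.5.1 is generic shorthand. It describes baseline characteristics in similar terms (means, medians, SDs, IQRs), although section 2.4.3 counts gender and job among them, and nobody would report a median job. On this view the choice between a percentage and a median for each item belongs to an analysis plan or table shells, and a competent analyst would report a percentage anyway. Part of this stands: it lowers the weight of the point. It does not remove it, because the outcome sentence names antidepressant use and prescribes its summary, so reporting a percentage alone would depart from the written rule.

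The reply is also right that the figures depend on a coding that the protocol does not state. Under dose coding they do not carry over. The 49 is a recruitment target within a maximum of 77, so the bands are illustrative.

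A reader might go further and infer that, whatever the coding, separate baseline and follow-up summaries cannot show who started or stopped. The documents do not support that. Sections 2.4.1 and 6.4.1 speak of collecting change itself, so the follow-up item may ask about it directly. The questionnaires are not shown, and section 6.5.1 does not rule out further tables.

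**Conclusion.** The point holds as a minor wording error. Section 6.5.1 fixes a summary for antidepressant use that, under yes/no coding, does not report the proportion using. With 49 care-as-usual participants, 27% and 49% users cannot be told apart under most quantile definitions. The result rests on two assumptions: yes/no coding, and the planned group size being reached.

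It would be a mistake to infer that the feasibility study or the later trial is compromised. No feasibility, acceptability or contamination conclusion depends on this variable. The version control table (v1.3) gives hours until return to work as the agreed primary outcome of the definitive trial, and section 6.5.1 summarises days to normal working hours separately. Sections 6.1 and 7.0 speak of outcome measures in general and do not name antidepressant use as a power input. The proportion can be recovered from the data at any time. Nor is there any fault in applying the rule to the symptom and quality-of-life scores.

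**What to change.** In section 6.5.1, remove antidepressant use from the mean-or-median sentence. State instead that the number and percentage using will be reported at baseline, 3 and 6 months, each with its missing-data count. State the coding too. If dose or number of drugs is recorded, that can be summarised among users beside the percentage.

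Because section 6.4.1 lists change in use as a possible outcome, add a table of participants who started, stopped, stayed on and stayed off between baseline and follow-up, among those with records at both times.

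The cost is a sentence or two and a few table rows, assuming that the item is asked at all three questionnaire times. The one drawback is that the table of changes leaves out people with no follow-up record. The percentages at each time and the missing-data counts must therefore stand beside it, with a note saying so.
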